6.1 Primary efficacy objective

To evaluate the effect of LCZ696 on cardiopulmonary exercise test (CPET) parameters in patients with non-obstructive HCM.

6.1.1 Variable

The primary efficacy variable/endpoint is the change from baseline in peak VO₂ (ml/kg/min) at Week 50.

6.1.2 Descriptive analyses

The raw peak VO₂ measurements, the change from baseline in peak VO₂ measurements and the ratio to baseline in peak VO₂ measurements will be listed by treatment, patient and visit/time.

Descriptive statistics will be provided for the raw peak VO₂ measurements, the change from baseline in peak VO₂ measurements and the ratio to baseline in peak VO₂ measurements by treatment and visit/time and will include sample size, mean (arithmetic), SD, median, minimum and maximum.

6.1.3 Graphical presentation

N/A.

6.1.4 Statistical model, assumptions and hypotheses

The effect of LCZ696 on the change from baseline in peak VO₂ over time (with Week 50 being of primary interest) will be analyzed using a longitudinal mixed effects model with change from baseline in peak VO₂ as the dependent variable. The model will include treatment, time (as a categorical variable relative to start of study treatment, i.e., Week 26 and Week 50), and the treatment-by-time interaction as fixed effects, patient as a random effect, and baseline peak VO₂ and the baseline-by-time interaction as covariates. Kenward-Roger method will be used for approximating the denominator degrees of freedom. The least-squares (LS) mean and associated 2-sided 90% confidence interval (CI) of the change from baseline in peak VO₂ for each treatment, and the estimated mean treatment difference, the p-value, and the corresponding 2-sided 80% CI will be extracted from the model at each time point.

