12.7 Interim analyses

An interim analysis for safety and efficacy will be performed when approximately 20 patients have completed the Week 26 CPET assessment. The same analysis described for the primary analysis will be performed using all the available CPET data at the time of the interim database freeze. Unblinded results will be reviewed by the clinical team. The clinical team may communicate the results (e.g., evaluation of PoC criteria or information needed for planning/modifying another study) to relevant Novartis teams for information, consulting, and/or decision purposes. Additional interim analyses may be conducted to support decision making concerning the current clinical study, the sponsor's clinical development projects in general, or in case of any safety concerns.

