12.8 Sample size calculation

12.8.1 Primary endpoint(s)

Approximately forty-four (44) patients will be enrolled in the study with the anticipation that at least 40 patients complete the study. With 40 completers, there will be 80% power to achieve

an efficacy criteria of at least 50% confidence that LCZ696 increases peak VO₂ by at least 3 ml/kg/min over placebo, provided that the true effect of LCZ696 is at least a 4.15 ml/kg/min increase over placebo and the standard deviation of the change from baseline is 4.25 ml/kg/min (Olivotto et al 2018). If LCZ696 is not different from placebo, there will be a 1.5% chance of achieving the efficacy criteria (i.e., the false positive rate will be 1.5%). For the interim analysis, with week 26 data from at least 20 patients, there will be 70% power to meet the efficacy criteria under the same assumptions, and a 6% false positive rate if there is no increase over placebo.

13 Ethical considerations and administrative procedures

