Potassium	≤ 5.2 mmol/L (mEq/L)	≤ 5.4 mmol/L (mEq/L)
eGFR	≥ 30 mL/min/1.73m ²	≥ 25 mL/min/1.73m ²
Blood Pressure	SBP ≥ 100 mmHg	No symptomatic hypotension as determined by the investigator and SBP ≥ 100 mmHg
AEs / Med History	No conditions that preclude continuation according to the eligibility criteria	No AEs that preclude continuation according to the investigator's judgment

Note that for abnormalities in potassium and eGFR, laboratory values should be repeated to confirm abnormality as outlined in protocol Section 16.3 and Section 16.4. For out-of-range blood pressure readings, measurement may be repeated up to two times as detailed in the Site Operations Manual and protocol Section 16.5.

Patients will receive study treatment for ~50 weeks, which includes the 4-week treatment run-in period, with dose tolerability being assessed at each visit as well as at unscheduled visits (as necessary) and through feedback that patients may provide between visits. Safety and tolerability assessments will include physical examinations, ECGs, vital signs, standard clinical laboratory evaluations (hematology and blood chemistry), AE and SAE monitoring. At week 26 and week 50, patients will have follow-up CPET [REDACTED]. No further treatment will be provided after the week 50 visit, and patients will return to the study center ~30 days later for final safety and EOS evaluations.

Figure 1-1 Study design

2 First interpretable results (FIR)

First interpretable results (FIR) will be provided for this trial at the IA and at the end of study (CSR).

The study FIR template (mock slides) can be found in SubWay in the study Statistics folder.

The template shows the analysis / results to be presented in the FIR. Study outputs required to be created at the time of the FIR will be highlighted in TFL shells document and marked as “Key” in the Programming Deliverables Tracker (PDT) output list.

3 Interim analyses

An interim analysis for safety and efficacy was performed when approximately 20 patients had completed the Week 26 [REDACTED]. [REDACTED]
[REDACTED]
[REDACTED]

[REDACTED] Unblinded results were reviewed by the clinical team. The clinical team may communicate the results (e.g., evaluation of PoC criteria or information needed for

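### As written, the primary model assumes the change in peak VO2 is equally variable at Week 26 and Week 50. If it is not, the Week 50 intervals and p-value are miscalibrated, though the point-estimate success rule is essentially unaffected.

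*SAP*

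**What the plan says.** SAP 6.1.4 fits a longitudinal mixed model to the change from baseline in peak VO2 at two visits, Week 26 and Week 50. Fixed effects are treatment, visit and their interaction; baseline and baseline-by-visit are covariates. The only within-patient term is the patient effect: "interaction as fixed effects, patient as a random effect". Protocol 12.4.2 uses the same words, without the baseline-by-visit term. Neither section states a residual covariance or visit-specific variances.

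On inference, the SAP adds that the "Kenward-Roger method will be used for approximating the denominator degrees of freedom". Each arm's LS mean gets a two-sided 90% interval. For the treatment difference, the p-value and the "corresponding 2-sided 80% CI will be extracted from the model at each time point".

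No supportive analysis in SAP 6.1.5 relaxes the covariance. The log-ratio model repeats the patient-effect wording, and the other two reuse the 6.1.4 model.

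Protocol 12.8.1 plans on a single SD of change, 4.25 ml/kg/min, and carries it to the Week 26 interim: "70% power to meet the efficacy criteria under the same assumptions". Protocol 12.7 applies the same model at the interim: "The same analysis described for the primary analysis will be performed using all the available CPET data".

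**The concern.** A random intercept with one residual variance gives the same total variance at both visits. With two visits, the model therefore pools the Week 26 and Week 50 residual variances and uses the average for the Week 50 comparison. If Week 26 is less variable than Week 50, the Week 50 interval is too narrow and the p-value too small. If Week 26 is more variable, the reverse holds. Kenward-Roger allows for the covariance parameters being estimated; it does not repair a structure that is wrong.

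At stake are the main inferential outputs of the primary analysis: the Week 50 p-value, the 80% interval for the difference and the 90% intervals per arm. SAP 6.1.2 reports descriptive statistics "by treatment and visit/time and will include sample size, mean (arithmetic), SD, median, minimum and maximum", so a reader could see unequal SDs, but nothing in the plan would correct the interval.

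**Working it through.** **Inputs from the documents.** Allocation is 1:1 with 40 completers, taken as 20 per arm. The SD of change is 4.25, the threshold 3, the assumed true effect 4.15, and 44 patients are enrolled (Protocol 12.8.1; allocation from Table 4-1). **Assumptions.** The Week 26 SD is varied from 3.0 to 5.0 (to 5.3 in the last missing-data check), because no visit-specific value is given. The within-patient correlation is 0.6, varied below. SDs are residual SDs after treatment and baseline; it is their ratio that drives the result.

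**1. The plan's own figure.** At least 50% confidence in an effect of 3 is the same as a point estimate of at least 3.
- SE = 4.25 × sqrt(2/20) = 1.344.
- Power = Φ((4.15 − 3)/1.344) = Φ(0.856) = 80.4%, against 80% stated.
- False positive rate = 1 − Φ(3/1.344) = 1.3% (1.6% with a t distribution), against 1.5% stated.

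The plan's figures reproduce.

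**2. What the model does to the standard error.** With complete data and both treatment and baseline interacting with visit, the Week 50 estimate equals that from a Week 50 ANCOVA. Its variance is built on (s26² + s50²)/2 instead of s50². The ratio of model SE to true SE is therefore

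sqrt((SD26² + SD50²)/(2·SD50²)).

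For SD26 = 3.0: sqrt((9 + 18.0625)/36.125) = 0.866. For SD26 = 4.675: sqrt((21.856 + 18.0625)/36.125) = 1.051.

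**3. Coverage and test size at Week 50** (100,000 simulated complete-data trials per row). The random-intercept analysis uses the averaged variance with df = 2·37/(1 + r²), about 54 at r = 0.6. The unstructured analysis uses the Week 50 variance on 37 df.

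| Week 26 SD | SE ratio | Coverage of nominal 80% CI, random intercept | Rejection rate, nominal two-sided 5% test |
|---|---|---|---|
| 3.0 | 0.866 | 73.3% | 9.0% |
| 3.4 | 0.906 | 75.4% | 7.5% |
| 3.825 (−10%) | 0.951 | 77.7% | 6.3% |
| 4.25 | 1.000 | 80.0% | 5.2% |
| 4.675 (+10%) | 1.051 | 82.3% | 4.0% |
| 5.0 | 1.092 | 83.7% | 3.4% |

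Unstructured covariance covers 80.0–80.2% in every row. Correlation hardly matters: at 0.4 and 0.8, random-intercept coverage is 75.2% and 75.2% for SD 3.4, and 83.4% and 83.6% for SD 5.0. The 5% level is a yardstick; the plan sets no significance level.

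**4. The success rule.** With complete data the point estimate is the same under both covariances. The chance of an estimate of at least 3 stays at 80% for a true effect of 4.15 and at 1.3–1.4% for no effect.

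**5. Missing Week 50 data.**
- *Moderate MAR.* 22 per arm, 9–12% missing at Week 50 depending on the Week 26 change, REML with Satterthwaite df, 1,500 trials per setting (Monte Carlo SE about 1 point). Coverage, random intercept / unstructured, is 73.8/80.5% (Week 26 SD 3.0), 76.5/79.9% (3.825), 82.3/80.4% (4.675) and 84.9/81.3% (5.0). The two estimates differ by 0.03–0.08 ml/kg/min on average, and the decision on the threshold of 3 agrees in 98.5–99.5% of trials.
- *Extreme MAR.* 4 of 44 missing, all of them the lowest Week 26 values in the LCZ696 arm (2,500 trials per setting). The random-intercept estimate shifts by +0.29 (Week 26 SD 3.0) or −0.20 (5.3). The chance of success is 86.0% against 80.2% unstructured, or 76.2% against 79.9%.

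**The case against.** **No evidence of unequal variances.** The only planning value is one SD used for both visits, and a common-variance model agrees with it. Both follow-up exercise tests come after the scheduled titration, so nothing in the design points to a large change in spread. The most striking figures come from a Week 26 SD about 29% below the protocol's. This stands as a limit on size: the 10% rows are the more moderate guide, and they amount to about 2 points of coverage. It does not support the equal-variance assumption, which the documents do not justify either.

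**The structure is inferred from silence.** The programs may use visit-specific variances. That is possible, but the SAP is the document that says how the primary analysis is carried out, and it goes as far as naming the degrees-of-freedom method. Its ordinary reading is a single residual variance.

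**No decision depends on it.** The one stated criterion is a point-estimate rule, and no threshold is attached to the p-value or intervals. This largely stands and keeps the point from being more serious. The rule's immunity is exact only with complete data.

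**The formula uses residual variances.** This is correct. The SDs reported under SAP 6.1.2 are unadjusted and would show the problem only approximately.

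**Changing the primary model after the interim is itself a risk.** SAP Section 3 records that "Unblinded results were reviewed by the clinical team", and Protocol 6.4 lets the statisticians see treatment codes throughout. Adding the unstructured model only as a sensitivity analysis is a defensible alternative, but it leaves the primary interval dependent on the untested assumption. The SAP already departs from Protocol 12.4.2 by adding the baseline-by-visit term. The risk is a reason to document the change and report both models.

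**Conclusion.** The concern holds. As specified, the primary model assumes equal residual variance at the two visits, and no planned analysis relaxes this. If the assumption fails, the Week 50 intervals and p-value are miscalibrated. Whether it fails, and in which direction, cannot be told from the documents. A 10% difference in SD costs about 2 points of coverage on the 80% interval; a Week 26 SD of 3.0 against 4.25 costs nearly 7. These figures rest on 20 per arm and an assumed correlation of 0.6, to which they are insensitive.

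The success rule and the stated 80% power are unaffected with complete data and nearly so under moderate dropout. Only extreme dropout confined to one arm moved the success probability, by about 4 to 6 points. The change is worth making because it is cheap and protects the primary interval; the go/no-go rule is not in serious doubt.

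**What to change.** In SAP 6.1.4 and the 6.1.5 models, specify an unstructured within-patient covariance for Week 26 and Week 50 (two variances and one covariance) with Kenward-Roger. It should replace the random patient effect, not be added to it. Fall back to the random-intercept model only on non-convergence. Report the random-intercept model as a sensitivity analysis. Record the change before database lock as a departure from Protocol 12.4.2 made after the unblinded interim, with the reason.

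The cost is a short SAP amendment, one code statement and one extra output. There is one more variance parameter: with complete data the 80% t multiplier rises from 1.297 (54 df) to 1.305 (37 df), and 1.305/1.297 = 1.006, so the interval is about 0.6% wider when the variances are in fact equal.

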6.1.4.1 Handling of missing data

There will be no imputation of missing data. The primary model implicitly imputes missing measurements under a missing at random assumption.

6.1.4.2 Graphical presentation of results

The least-squares (LS) arithmetic mean treatment estimates (+/- 90% CI) will be plotted over time and by treatment using line plots (all treatments in the same graph). Baseline will also be presented as 0 in this model-based plot for better visualization of the changes from baseline over time.

6.1.5 Sensitivity and supportive analyses

The following two supportive analyses will be performed to further assess the effect of LCZ696 on changes in peak VO₂:

(1) An analysis of the ratio to baseline in peak VO₂. A similar model to that described in [Section 6.1.4](#) for the primary analysis will be used, but with ratio to baseline as the response, and all peak VO₂ measurements will be log transformed prior to analysis. In particular, ratio to baseline in peak VO₂ over time (with Week 50 being of primary interest) will be analyzed using a longitudinal mixed effects model with log-transformed ratio to baseline in peak VO₂ as the dependent variable. The model will include treatment, time (as a categorical variable relative to start of study treatment, i.e., Week 26 and Week 50), and the treatment-by-time interaction as fixed effects, patient as a random effect, and the log-transformed baseline peak VO₂ and the log-transformed baseline-by-time interaction as covariates. Kenward-Roger method will be used for approximating the denominator degrees of freedom. The LS mean and associated 2-sided 90% CI of the ratio to baseline in peak VO₂ for each treatment, on the log scale, will be extracted from the model at each time point, along with the estimated mean treatment difference, the p-value, and the corresponding 2-sided 80% CI. The means and CIs will be back transformed and reported as geometric mean ratios or ratios of geometric mean ratios on the original scale.

(2) The same model as described in [Section 6.1.4](#) for the primary endpoint will be used, but it will be performed on the RAS.

(3) The same model as described in [Section 6.1.4](#) for the primary endpoint will be used, but only patients who have RER > 0.95 at baseline, Week 26 and Week 50 time points will be analysed.

6.1.5.1 Handling of missing data

It is described in [Section 6.1.4.1](#).

6.1.5.2 Graphical presentation of results

[figure not shown]
For the change from baseline model, i.e., supportive model (2), the model-based graphs are described in [Section 6.1.4.2](#).

[figure not shown]
For the log-transformed ratio to baseline model, i.e., supportive model (1), the least-squares (LS) geometric mean treatment estimates (+/- 90% CI) will be plotted over time and by treatment using line plots (all treatments in the same graph). Baseline will also be presented as 1 in this model-based plot for better visualization of the ratios to baseline over time.

[figure not shown]
6.2 Secondary efficacy objectives

[figure not shown]
There are no secondary efficacy objectives for this study.

[figure not shown]
The secondary objectives of this study are related to the safety and tolerability of LCZ696 and are described in [Section 7](#).

[figure not shown]

[figure not shown]

7 Statistical methods for safety and tolerability data

Unless specified otherwise, all safety analyses will be presented separately for the treatment run-in period and the double-blind placebo-controlled randomized treatment period, using the safety analysis set.

7.1 Variables

Adverse events, body height, body weight, BMI, vital signs (blood pressure, pulse rate and oral body temperature), ECG intervals (PR interval, QRS duration, heart rate, RR interval, QT interval and QTcF), laboratory measurements, as well as patient demographics, baseline characteristics, and treatment information.

7.2 Descriptive analyses

Patient demographics and other baseline characteristics

All data for background and demographic variables including disease characteristics (age, gender, race, ethnicity, height, weight, BMI, systolic blood pressure, diastolic blood pressure, NT-proBNP, peak VO₂, % of predicted peak VO₂ and NYHA class) will be listed by treatment and patient. Summary statistics will be provided by treatment for the RAS. Categorical data will be presented as frequencies and percentages. For continuous data, sample size, mean (arithmetic), SD, median, minimum and maximum will be presented. The same summary table will be created to compare the treatment run-in failure patients vs. the randomized patients for the safety analysis set.

Relevant medical history, current medical conditions, results of laboratory screens and any other relevant information will be listed by treatment and patient. Relevant medical histories and current medical conditions at baseline will be summarized by system organ class (SOC) and preferred term (PT), by treatment for the RAS. A patient with multiple relevant medical histories/current medical conditions within a system organ class (SOC) is only counted once towards the total of this system organ class (SOC).

Treatment

Data for study drug administration (rescue medication) as well as concomitant medications and significant non-drug therapies prior to and after the start of the study treatment will be listed by treatment and patient.

Concomitant medications and significant non-drug therapies prior to and after the start of the study treatment will be summarized by Anatomical Therapeutic Chemical (ATC) class and treatment for the RAS. A patient with multiple concomitant medications/significant non-drug therapies within an Anatomical Therapeutic Chemical (ATC) class is only counted once towards the total of this Anatomical Therapeutic Chemical (ATC) class.

Overall compliance to the study drug administration

Overall compliance to the study drug administration* will be listed by treatment and patient and summarized by treatment for the RAS.

Note: Any compliance values >100% will be set to and used as 100% in summary statistics.

*For each patient, the overall compliance to study drug (%) will be calculated using the following formula:

$$100 * \left[\frac{\sum_{i=1}^n (Number\ of\ pills\ dispensed\ at\ V_{i-1} - Number\ of\ pills\ returned\ at\ V_i)}{\sum_{i=1}^n ((Study\ day\ at\ V_i - Study\ day\ at\ V_{i-1}) * 2\ pills\ per\ day)} \right]$$

where,

V_0 = first visit of study drug administration,

V_1 = second visit of study drug administration,

.

.

V_{n-1} = second – to – last visit of study drug administration, and

V_n = last visit of study drug administration.

Time weighted average daily dose

Time weighted average daily dose* will be listed by treatment and patient for the RAS and summarized by treatment for both the RAS and the PPS separately. Only patients randomized to the LCZ696 treatment will be included in this analysis.

*For each patient, the time weighted average daily dose will be calculated over the randomization period using the following formula:

$$\left[\frac{\sum_{i=1}^n (days\ of\ dosing_i^a * corresponding\ dose_i\ (in\ mg) * 2)}{days\ in\ the\ randomization\ period^b} \right]$$

where,

$a = Last\ study\ day\ of\ dose_i - first\ study\ day\ of\ dose_i + 1$

Note: During the transition from the previous dose to the next dose, we consider that the next dose starts one day after the end study day of the previous dose, i.e., if the previous dose ended on study day x, then the next dose is considered to start on study day x+1 even if the next dose started on study day x as per the data.

$b = Last\ study\ day\ of\ the\ randomization\ period - first\ day\ of\ the\ randomization\ period + 1$

Vital signs

All vital signs data will be listed by treatment, patient, and visit/time and if ranges are available, abnormalities (and relevant orthostatic changes) will be flagged. Summary statistics will be provided by treatment and visit/time and will include sample size, mean (arithmetic), SD, median, minimum and maximum.

ECG evaluations

All ECG data will be listed by treatment, patient, and visit/time, and abnormalities will be flagged. Summary statistics will be provided by treatment and visit/time and will include sample size, mean (arithmetic), SD, median, minimum and maximum.

Clinical laboratory evaluations

All laboratory data will be listed by treatment, patient, and visit/time and if normal ranges are available abnormalities will be flagged. A separate listing will be provided presenting all parameters in a patient with any abnormal values. Summary statistics will be provided by treatment and visit/time and will include sample size, mean (arithmetic), SD, median, minimum and maximum. Shift tables using the low/normal/high classification will be used to compare baseline to the worst on-treatment value.

Adverse events

All information obtained on adverse events will be listed by treatment and patient. If any death occurs, then all deaths will be listed by treatment and patient

The treatment emergent AEs are defined as follows for this study:

- For the **treatment run-in period**: Treatment emergent AEs will be the events that started at or after the first dose of study medication and before the start of the double-blind treatment period or events present prior to first dose of study medication but increased in severity during the treatment run-in period based on preferred term.
- For the **randomized treatment period**: Treatment emergent AEs will be the events that started at or after the start of the double-blind treatment period or events present prior to the start of double-blind treatment period but increased in severity based on preferred term.

The number and percentage of patients with treatment emergent AEs will be summarized in the following ways:

- by treatment, primary system organ class (SOC), and preferred term (PT).
- by treatment, primary system organ class (SOC), preferred term (PT), and maximum severity.
- by treatment, Standardized MedDRA Query (SMQ), and preferred term (PT).

Separate summaries will be provided for study related adverse events, serious adverse events and adverse events leading to drug discontinuation.

A patient with multiple adverse events within a primary system organ class (SOC) is only counted once towards the total of the primary system organ class (SOC).

ClinicalTrials.gov and EudraCT

For the legal requirements of ClinicalTrials.gov and EudraCT, two required tables on <on-treatment/treatment emergent> adverse events which are not serious adverse events with an incidence greater than 5% and on <on-treatment/treatment emergent> serious adverse events

and SAE suspected to be related to study treatment will be provided by system organ class and preferred term on the safety set population.

If for a same patient, several consecutive AEs (irrespective of study treatment causality, seriousness and severity) occurred with the same SOC and PT:

- a single occurrence will be counted if there is ≤ 1 day gap between the end date of the preceding AE and the start date of the consecutive AE
- more than one occurrence will be counted if there is > 1 day gap between the end date of the preceding AE and the start date of the consecutive AE.

[figure not shown]
For occurrence, the presence of at least one SAE / SAE suspected to be related to study treatment / non SAE has to be checked in a block e.g., among AE's in a ≤ 1 day gap block, if at least one SAE is occurring, then one occurrence is calculated for that SAE.

[figure not shown]
The number of deaths resulting from SAEs suspected to be related to study treatment and SAEs irrespective of study treatment relationship will be provided by SOC and PT.

[figure not shown]

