16.1 Appendix 1: Clinically notable laboratory values

Clinically notable laboratory abnormalities for selected tests based on a percent change from baseline:

Hematology

- Hematocrit >50% increase, >20% decrease
- Hemoglobin >50% increase, >20% decrease
- Platelet count >75% increase, >50% decrease
- RBC Count >50% increase, >20% decrease
- WBC count >50% increase, >50% decrease

Blood Chemistry

- Alkaline phosphatase >100% increase
- ALT (SGPT) >150% increase
- AST (SGOT) >150% increase
- BUN >50% increase
- Calcium >10% increase, >10% decrease
- Chloride >10% increase, >10% decrease
- Creatinine >50% increase
- Potassium >20% increase, >20% decrease
- Total bilirubin >100% increase
- Uric acid >50% increase

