- Consider down-titration of study drug, according to investigator's medical judgment.

Serum potassium greater than 5.5 and less than 6.0 mmol/L (mEq/L)

- Confirm potassium concentration in a non-hemolyzed sample.
- Consider down-titration or temporarily discontinue study drug according to investigator medical judgment.
- Apply all measures outlined for serum potassium > 5.3 and ≤ 5.5 mmol/L
- Repeat serum potassium measurement after 2-3 days
- If serum potassium < 5.5 mmol/L, consider resumption of study drug at lower dose with repeat potassium within 5 days.

Serum potassium greater than or equal to 6.0 mmol/L (mEq/L)

- Immediately discontinue study drug
- Confirm potassium concentration in a non-hemolyzed sample
- Urgently evaluate patient and treat hyperkalemia as clinically indicated
- Apply all measures outlined for serum potassium > 5.3 and < 6.0 mmol/L (mEq/L)

No resumption of study drug without individualized case discussion with and permission from Novartis medical monitor or his/her designee.

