7.3 Graphical presentation

A boxplot of the raw vital signs data (sitting pulse rate, sitting systolic blood pressure and sitting diastolic blood pressure) and an arithmetic mean (SE) plot of changes from baseline in vital signs data (sitting pulse rate, sitting systolic blood pressure and sitting diastolic blood pressure) to visualize trends in longitudinal safety data will be created by treatment and over time. Baseline will also be presented as 0 in the arithmetic mean (SE) plot for better visualization of the changes from baseline over time.

In addition, spaghetti plots of vital signs of interest (i.e., sitting systolic blood pressure and sitting diastolic blood pressure) and biochemistry lab parameters of interest (i.e., creatinine, eGFR, potassium and urea nitrogen) will be created by treatment. Note: Only the patients with at least one unscheduled assessment related to AE will be included in the spaghetti plots and all the measurements (scheduled, repeated & unscheduled) of these patients will be presented.

10 Reference list

1. Clinical Trial Protocol, CLCZ696I12201, Protocol Version 02, dated 08 Apr 2022.
2. Site Operations Manual for Protocol No. CLCZ696I12201, Version 06, dated 26 Jan 2022.

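### The visible SAP plans no by-arm count of patients crossing the protocol's own potassium, eGFR and creatinine criteria, so crossings not reported as adverse events are not counted

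*SAP*

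**What the plan says.** Safety and tolerability is the only secondary objective, and safety laboratory tests are among its endpoints (SAP 1.3.2).

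**Laboratory outputs.** SAP 7.2, following protocol 12.5.1, plans:
- Listings: "All laboratory data will be listed by treatment, patient, and visit/time and if normal ranges are available abnormalities will be flagged". The SAP adds a listing of all parameters for any patient with an abnormal value.
- Visit statistics: "Summary statistics will be provided by treatment and visit/time and will include sample size, mean (arithmetic), SD, median, minimum and maximum".
- Shift tables: "Shift tables using the low/normal/high classification will be used to compare baseline to the worst on-treatment value".

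SAP 7.3 adds individual-patient plots of creatinine, eGFR, potassium and urea nitrogen, with a filter: "Only the patients with at least one unscheduled assessment related to AE will be included in the spaghetti plots".

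**Adverse event outputs.** "The number and percentage of patients with treatment emergent AEs will be summarized in the following ways": by system organ class and preferred term, by maximum severity, and by SMQ. Related events, serious events and events leading to drug discontinuation are summarised separately.

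**The protocol's own laboratory criteria.**
- Appendix 4 sets potassium action bands: above 5.3 to 5.5, above 5.5 to below 6.0, and "Serum potassium greater than or equal to 6.0 mmol/L (mEq/L").
- Appendix 3 sets eGFR falls from screening/baseline of at least 25% (surveillance) and at least 40% (action), with creatinine levels of 2.5 and 3 mg/dL as alternatives.
- Section 10.2.2 calls a creatinine rise of at least 25% a renal event.
- Table 3-1 sets on-treatment limits of potassium no higher than 5.4 mmol/L and eGFR no lower than 25.
- Appendix 1 lists "Clinically notable laboratory abnormalities for selected tests based on a percent change from baseline", for example potassium by more than 20% and creatinine by more than 50%.

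The visible SAP text tabulates none of these by arm.

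**The concern.** Protocol 4.7 names hyperkalemia as a risk of the drug. It relies on monitoring blood pressure, potassium and creatinine to decide on down-titration or withdrawal. The criteria that drive those decisions are numeric, and the planned by-arm laboratory comparison does not use them.

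The route from a laboratory value to a by-arm count runs through adverse event reporting. Under protocol 10.1.1 an abnormal value is an adverse event only if it causes signs or symptoms, is judged clinically significant, or needs therapy. A surveillance-level eGFR fall, or a creatinine rise meeting the 10.2.2 definition, may be repeated and watched without meeting any of these. The arms could then differ in protocol-defined laboratory events with no planned table giving the numbers.

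The plot filter works the same way. A patient whose potassium rise was found at a scheduled visit, or whose repeat test was not linked to an adverse event, is left out of the figure meant to show these parameters.

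**Working it through.** The plan states no figure on this point, so there is none to reproduce. The check is whether the shift-table cells can separate the protocol's criteria. The documents give no reference limits, so a range is assumed.

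**Potassium (mmol/L).** Cell of the worst value under assumed upper limits:

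| Worst value | Appendix 4 band | Limit 5.0 or 5.1 | Limit 5.2 or 5.3 | Limit 5.5 |
|---|---|---|---|---|
| 5.2 | none | high | normal | normal |
| 5.4 | >5.3 to 5.5 | high | high | normal |
| 5.6 | >5.5 to <6.0 | high | high | high |
| 6.2 | 6.0 or more | high | high | high |

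With any limit from 5.0 to 5.3, three action bands share one cell. With 5.5, the lowest band reads normal and the upper two still share a cell.

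**eGFR (mL/min/1.73m²).** Fall = (baseline − worst) / baseline, with an assumed lower limit of 60 or 90:

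| Baseline to worst | Fall | Protocol criterion | Limit 60 | Limit 90 |
|---|---|---|---|---|
| 50 to 45 | 5/50 = 10% | none | low-to-low | low-to-low |
| 50 to 37 | 13/50 = 26% | surveillance | low-to-low | low-to-low |
| 50 to 29 | 21/50 = 42% | action | low-to-low | low-to-low |
| 31 to 24 | 7/31 = 23% | below Table 3-1 limit | low-to-low | low-to-low |
| 120 to 70 | 50/120 = 42% | action | normal-to-normal | normal-to-low |

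Entry is allowed from an eGFR of 30, so a low baseline is possible. A 10% and a 42% fall from 50 give the same cell under both limits.

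**Percent-change criteria.** The 10.2.2 creatinine rise and the Appendix 1 changes are within-patient percentages. A reference-range category does not encode them, and the minimum and maximum at a visit do not show change within a patient.

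**What counts could show.** With 44 randomised 1:1, each arm has about 44/2 = 22 patients. The chance of at least one event in an arm is 1 − (1 − p)^22. For assumed true rates:
- 2%: 36%
- 5%: 68%
- 10%: 90%
- 20%: 99%

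Exact 95% limits are 0 to 15% for 0/22, 0.1 to 23% for 1/22 and 3 to 35% for 3/22. The counts would describe the data and would not support a firm between-arm inference.

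**Cut-offs that conflict within the protocol.**
- The Appendix 4 title starts at 5.3 or more, but its text starts above 5.3.
- Its range of concern starts at 5.5 or more, but the matching action band starts above 5.5.
- Table 3-1 accepts values up to 5.4, which overlaps the lowest action band.

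A value of exactly 5.3, 5.4 or 5.5 is therefore classified differently depending on the passage used.

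**The case against.** The strongest reply is that the main clinical events are already counted. Treatment-emergent adverse events are tabulated by arm, including by SMQ, and those leading to discontinuation are shown separately. Protocol 8.4.4 requires every abnormal laboratory result to be assessed against the adverse event criteria, and 10.1.1 points to Appendix 1 for that review. In a trial of about 44 patients the listings hold every value by arm and patient, and visit extremes are reported. Appendices 3 and 4 are management guidance, not endpoints, and the SAP follows protocol 12.5.1.

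Much of this stands. A reader might infer that the trial has no by-arm count of hyperkalemia, renal impairment or hypotension. The documents do not support that, because the adverse event tables provide one. Nor do they support the inference that a potassium of 6.0 or more would pass unnoticed. Appendix 4 requires study drug to be stopped at once and the patient treated as clinically indicated, so the event would very probably be reported as an adverse event.

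The reply does not cover crossings that are not reported as adverse events, since that status rests partly on investigator judgment. For liver tests, protocol 10.2.1 itself treats laboratory triggers separately from adverse event status. Listings allow a hand count after unblinding, but that is not a planned summary. Repeat tests required by Appendices 3 and 4 bring a patient into the plots only if linked to an adverse event.

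Absence is shown only for the visible text. SAP 1.1 places table shells in a separate document, and parts of both documents are redacted, so such a table may exist elsewhere.

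**Conclusion.** This is a cheap improvement, not a defect that undermines the safety objective. The visible SAP plans no number and percentage of patients by arm at the protocol's own laboratory criteria, and the low/normal/high tables cannot supply one. Potassium bands merge for every assumed upper limit from 5.0 to 5.5. A 42% eGFR fall from 50 reads low-to-low with a lower limit of either 60 or 90. What goes uncounted is limited to laboratory-defined events not reported as adverse events.

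How many patients that is cannot be derived, because the documents give no rates. The cell examples rest on assumed reference limits, although the failure to separate the criteria holds across the ranges tried. The plot filter is stated outright and rests on no assumption.

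**What to change.** **SAP 7.2.** For the randomised period and by arm, add n (%) of patients by worst post-randomisation value, including unscheduled results, for:
- the Appendix 4 potassium bands;
- eGFR falls of at least 25% and at least 40%;
- a creatinine rise of at least 25% (protocol 10.2.2);
- the Appendix 3 creatinine limits;
- the Appendix 1 notable changes.

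**SAP 7.3.** Plot all patients and highlight those with an AE-related unscheduled assessment.

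**Settle first.**
- Reconcile the potassium cut-offs in the Appendix 4 title, its text and Table 3-1. Which limits apply is for the sponsor to decide; the table should then use them.
- State whether local results are used, and whether the 0.4 mmol/L plasma conversion in protocol 8.4.4 is applied before banding.
- State the reference value. Appendix 3 measures falls from the screening/baseline visit, while the SAP's baseline is the last value before the first dose.
- State whether a crossing counts on the first value or only once confirmed, since the protocol asks for repeat testing.

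**Cost.** One or two extra tables and a changed plot filter. No new assessments are needed, but local results can be used only if they are held in the database. The counts should be labelled descriptive.
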